7.7 ASSESSMENT OF ADVERSE EVENTS

The Investigator at each participating site is ultimately responsible for reporting AEs and complications. Medical and scientific judgment should be exercised in determination of the AE description while adhering to the provided definitions. The Investigator is required to complete the adverse event case report form (Adverse Event CRF see xxxxx) at each trial visit. The Adverse Event CRF for a given visit must report all adverse events that occurred since the last documented visit.

Description of each AE must be as follows: AE description, the date of onset, date of resolution, serious (yes/no; see Section 7.2), frequency of the event (single episode, intermittent, continuous), action taken (none, medical and/or surgical), relationship to device, relationship to the procedure, and seriousness criteria.

CAUSALITY:

The causal relationship of the AE to the device and the procedure should be rated as follows:

- Not Related: Evidence exists that the adverse event definitely has a cause other than the trial procedure or device (e.g., pre-existing condition or underlying disease, intermittent illness, or concomitant medication) and does not meet any other criteria listed. There is no relationship between the event and the device or procedure.

- Related: Evidence exists that the trial device or procedure caused the adverse event. There is a temporal relationship between the event onset and trial device or procedure. The subject's clinical state and concomitant therapies are ruled out as a cause.
- Unknown: There is no evidence or relevant data available to assess the relationship between the event and the device or procedure.

Adverse event outcome defined as follows:

- Recovered/Resolved (the subject fully recovered from the adverse event with no residual effect observed).
- Recovered/Resolved with Sequelae (the residual effects of the adverse event are still present and observable).
- Ongoing (The adverse event itself is still present and observable).
- Death.
- Explant.
- Ongoing at the time of trial exit
- Chronic Condition (e.g., Cancer, Shingles, Herpes)

Action Taken for Event (identify all that apply):

- None (no treatment was required).
- Medication required (prescription and/or over the counter medication was required to treat the adverse event).
- Hospitalization or Prolongation of Hospitalization Required (hospitalization was required or prolonged due to the adverse event)
- Surgical intervention (not involving the trial valve)
- Reoperation or explant of the trial valve
- Other (specify).

7.8 ELECTROCARDIOGRAMS

An ECG will be performed with the subject in supine position at, POD 180-240 (optional), and annually thereafter until the trial ends. An expert cardiologist knowledgeable in cardiac conduction disturbances will determine the cardiac rhythm, and assess the ECG as normal or abnormal, and will specify any clinically significant abnormal findings.

Any new or worsened cardiac conduction disturbance defined as new or worsened first degree atrioventricular (AV) block, second degree AV block (Mobitz I or Mobitz II), third degree AV block, incomplete right bundle branch block, right bundle branch block, intraventricular conduction delay, left bundle branch block, left anterior fascicular block, or left posterior fascicular block will be reported.

7.9 LABORATORY TESTING

Blood data (red blood count, white blood count, hematocrit, hemoglobin, platelet count, and plasma-free hemoglobin or haptoglobin or serum LDH) will be collected POD 180-240 (optional), POD 365-435, and annually thereafter until the trial ends.

For all measured blood parameters, individual results will be compared to documented normal ranges. The Investigator will determine for each parameter that is out-of-range whether the value is abnormal not clinically significant, or abnormal clinically significant. Since summary statistics involving laboratory parameters will be provided, an out-of-range value does not necessarily constitute an AE; other signs and symptoms must be taken into an account in order to report the occurrence of an AE.

Coagulation profile (which may include prothrombin time [PT], or partial thromboplastin time [PTT], or international normalized ratio [INR]) will be collected at the POD 180-240 (optional visit) and annually thereafter, coagulation profile will only be determined for subjects on anticoagulant therapy.

8.0 EFFECTIVENESS ASSESSMENTS

8.1 PERI-PROCEDURAL PARAMETERS

Device technical success was defined as the successful delivery and deployment of the trial valve with maximum of two attempts and subject leaving the OR with valve in place. In addition, cross-clamp and cardiopulmonary bypass times, and length of stay in the ICU will be documented.

Procedural success was defined as device technical success followed by the absence of adverse events resulting in device reoperation implant of permanent pacemaker (with baseline sinus rhythm and no other pre-existing conduction issues), or valve-related death within discharge or 10 days post index procedure, whichever comes first.

8.2 NYHA CLASSIFICATION

The percentage of subjects in each specific NYHA functional class and the change in NYHA classifications from screening will be analyzed at each time point where NYHA is obtained to evaluate if implanting the trial valve results in an improvement in NYHA classification.

8.3 HEMODYNAMIC PERFORMANCE

Echocardiography will be conducted at POD 180-240 (optional), POD 365-435 and annually thereafter until the trial ends. The Echocardiography Core Lab Manual is provided in XXX for specific information regarding the conduct of these procedures.

The echo core lab will determine: peak systolic and mean aortic valve gradient, EOA, EOA index, performance index, cardiac output, cardiac index, valvular regurgitation (including paravalvular leak), left and right atrial size, left and right ventricular size, left and right ventricular function, ventricular septal and left ventricular posterior wall thickness, cavitary thrombi or other masses, pericardial abnormalities (e.g., effusion) and aortic root diameter.

9.0 STATISTICAL METHODS

The following section describes only those activities that will be conducted after the approval of the study product. All detailed analyses conducted for the PMA submission are XXXX and a xxxx all post approval analyses.

9.1 STATISTICAL ANALYSIS

9.1.1 ANALYSIS POPULATION

There will be two analysis populations for the trial: the enrolled or intent-to-treat population and the valve implant or as-treated population. The valve implant population will include all subjects who receive the trial valve and leave the operating room with the trial valve in place.

The valve implant population will be used for all analyses of NYHA and echocardiographic data.

9.1.2 SAFETY ANALYSIS

The analyses of the safety data will be performed for enrolled (ITT) patients and all valve implant (as-treated) patients. However, the primary analysis population for all safety analyses will be the valve implant (as-treated) population.

9.1.2.1 Primary Safety Endpoints

For the safety endpoints listed in Section 2.1, the early adverse events within 30 days of implant will be reported as the number of events divided by the number of patients for the events. Linearized rates will be used to summarize adverse events for the late (>30 days) post-operative period. The linearized rates will be calculated as the number of late events divided by the total late-patient years.

Actuarial analysis using the Kaplan-Meier method will be used to estimate the probability of freedom from each primary safety endpoint. Primary analyses of the primary safety endpoints (post 30 days) will be based on linearized rates, which account for multiple

events from a single patient. Actuarial (Kaplan-Meier) analysis of the time to first event per patient will be provided as an additional analysis.

9.1.2.2 Other Safety Data

Percentages for the early events and linearized rates for the late events will be calculated for all complications. If valve malposition, valve instability, valve dislodgement or valve migration/embolization occurs, any consequent adverse events or procedures (e.g. coronary ostia blockage, mitral valve impingement, or abrasion, intraoperative intervention, or reoperation) will be noted and rates presented.

9.1.3 EFFECTIVENESS ANALYSIS

Subjects will be analyzed according to the NYHA classification preoperatively, at POD 31-46, POD 90-135, and annually post implant for 5 years. The distribution (numbers of subjects and percentages) in the various NYHA classes and the change from baseline (improved, same and worse) will be tabulated and stratified by baseline NYHA at each follow-up interval. Echocardiography data will be obtained preoperatively, intraoperatively, at discharge, POD 90-135, POD 180-240 (optional) and annually post implant until the trial ends. Descriptive statistics for the continuous echo variables (e.g. mean, standard deviation, and range) will be categorized by time interval and valve size. Regurgitation data will be summarized by counts and percentages at each severity level.

A comparison of all effectiveness data for the EDWARDS INTUITY valve will be made to current state of the art prosthetic heart valve literature published in peer reviewed journals at the time of PMA submission.

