During the pre-market phase of the TRANSFORM™ Trial, the EDWARDS INTUITY Valve System (EDWARDS INTUITY Aortic Valve, Model 8300ACA/8300ACD and EDWARDS INTUITY Delivery System, Model

8300DCA/8300DCD) was indicated for use in subjects with aortic stenosis or stenosis plus insufficiency of an aortic valve requiring a planned replacement of their native aortic valve. Post market, the trial device is indicated for the replacement of diseased, damaged, or malfunctioning native or prosthetic aortic valves.

Schedule of Visits

- Screening (Day -90 to Day -1)
- Operative procedure (Day 0)
- Discharge (Post-op – Day of Discharge)
- Postoperative day POD 36 (-5/+10 days; by phone)
- POD 105 (-15/+30 days);
- POD 195 (-15/+45 days); only for subjects with paravalvular leak >mild or an implant related new or worsened cardiac conduction disturbance¹ on 3-month electrocardiogram;
- POD 390 (-25/+45 days)
 - PO Year 2 (-60/+60 days)
 - PO Year 3 (-60/+60 days)
 - PO Year 4 (-60/+60 days)
 - PO Year 5 (-60/+60 days)
- Annually thereafter until the last subject completes 5-year follow-up visit
 - At the time of this protocol revision, all patients had completed these visits

Safety Endpoints

The primary safety endpoints consist of:

- All cause mortality
 - Trial valve-related mortality
- Valve thrombosis (trial valve)
- Thromboembolism
- All hemorrhage
 - Major hemorrhage
- All paravalvular leak (trial valve)
 - Major paravalvular leak (trial valve)
- Endocarditis (trial valve)
- Structural valve deterioration (trial valve)
- Non-Structural valve deterioration (trial valve)

¹ Defined as new or worsened first degree atrioventricular (AV) block, second degree AV block (Mobitz I or Mobitz II), third degree AV block, incomplete right bundle branch block, right bundle branch block, intraventricular conduction delay, left bundle branch block, left anterior fascicular block, or left posterior fascicular block, including block requiring permanent pacemaker implant.

- Valve Malposition
- Valve Migration/ embolization
- Valve Instability
- Valve Dislodgment
- Hemolysis
- Reoperation
 - Trial valve-related reoperation
- Explant
 - Trial valve explant
- Implant-related new or worsened cardiac conduction disturbance
 - requiring permanent pacemaker implant
 - not requiring permanent pacemaker implant

The Data Monitoring Committee (DMC) will conduct a final meeting after the last subject has completed their 5-year follow up

**Effectiveness
Endpoints**

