6.2.1 POD 195 VISIT (-15/+45 DAYS)

This visit is only required if echocardiography at three months showed a PVL >mild as determined by the Echo Core Lab or an implant-related new or worsened cardiac conduction disturbance.

These subjects will return for follow-up between POD 180 to 240 and the following assessments will be performed:

| | |
|--------------------------------------------------------------|--------------------------------------------------------------------------------------------------------------------------------------------------------------------------------------------------------------------|
| Subject status | |
| Date of Follow-Up | |
| NYHA Classification | |
| Echocardiography (TTE) | Peak and mean pressure gradients, EOA, EOA index, performance index, cardiac output, cardiac index, valvular regurgitation (including paravalvular leak) |
| Electrocardiogram | 12-Lead ECG (Cardiac Rhythm) |
| Anticoagulant therapy/Concomitant cardiovascular medications | Anticoagulants/anti-platelets and other Concomitant cardiovascular medications |
| Coagulation profile | May include PTT or PT or INR if subject is on anticoagulant therapy only |
| Laboratory Testing | WBC, RBC, hemoglobin, hematocrit, platelets, plasma-free hemoglobin (a 2 nd lab draw for plasma free hemoglobin is required within 48 hours if the first draw is >40mg/dl) or haptoglobin or serum LDH |
| Vital signs | Blood pressure, heart rate, weight |
| Adverse events/Complications | If applicable |

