6.2.4 VISIT WINDOWS

Visits must be scheduled for specific times before and after the date of the index procedure. It is important that this schedule is maintained for all subjects. To facilitate compliance, each visit has a visit window as described in Table 1 below. Visits not completed within these windows will be considered “done out of window.” Additional visits completed will be considered unscheduled visits. Trial visits should be scheduled as close to the early part of the visit window as possible so that if it is necessary to cancel and reschedule the visit, the visit may still be conducted within the required visit window.

Table 1: Follow-up Visit Days & Visit Windows

| Visit | Visit Window (Days) | Timing from Implant (Day 0) |
|-----------|---------------------|-----------------------------|
| POD 195* | - 15/+45 | Day 180 to Day 240 |
| POD 390 | - 25/+45 | Day 365 to Day 435 |
| PO Year 2 | - 60/+60 | Day 670 - 790 |
| PO Year 3 | - 60/+60 | Day 1035 - 1155 |
| PO Year 4 | - 60/+60 | Day 1400 - 1520 |
| PO Year 5 | - 60/+60 | Day 1765 - 1885 |

* Required for subjects with PVL >mild on POD 105 echocardiography as determined by the Echo Core Lab or an implant-related new or worsened cardiac conduction disturbance.

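### Section 9.1.3 puts the triggered POD 180-240 visit in the same echo series as the all-subject visits, so a PVL percentage tabulated there would overstate the cohort share.

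*Combined protocol and SAP*

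**What the plan says.** The protocol restricts the POD 195 visit in three places. The Synopsis visit schedule has it "only for subjects with paravalvular leak >mild or an implant related new or worsened cardiac conduction disturbance". Section 6.2.1 says "This visit is only required if echocardiography at three months showed a PVL >mild as determined by the Echo Core Lab", and adds an implant-related new or worsened conduction disturbance as the second trigger. The footnote to Table 1 in Section 6.2.4 repeats both, beginning "Required for subjects with PVL >mild on POD 105 echocardiography as determined by the Echo Core Lab". Section 6.2.1 fixes the window ("These subjects will return for follow-up between POD 180 to 240") and lists valvular regurgitation, including PVL, among the echo measurements taken there.

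The analysis section does not carry this restriction over. Section 9.1.3 reads "Echocardiography data will be obtained preoperatively, intraoperatively, at discharge, POD 90-135, POD 180-240 (optional) and annually post implant until the trial ends", so the visit is marked only as optional and sits between the all-subject POD 90-135 visit and the annual visits. The summaries then follow. For continuous variables: "Descriptive statistics for the continuous echo variables (e.g. mean, standard deviation, and range) will be categorized by time interval and valve size". For regurgitation: "Regurgitation data will be summarized by counts and percentages at each severity level", with neither an interval nor a denominator.

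The NYHA sentence in the same section omits POD 180-240, although Section 6.2.1 collects NYHA class at that visit. Section 9.1.5 rules out imputation. No visible text excludes the interval from the echo tables or labels it as a selected subset.

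**The concern.** PVL >mild is both a reason for attending the visit and one of the results tabulated from it. A percentage based on attendees describes a group chosen partly because the leak was already there. The percentages before and after it describe everyone with an echo at that visit. Set side by side, they invite a reader to see PVL worsen in mid-first-year and then recover, when part or all of the movement may come from the change in who was measured.

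This matters for this device. Regurgitation including PVL is an effectiveness measure (Section 2.2), and the device description presents the expandable frame as a means of controlling PVL (Section 1.2). Calling the visit optional adds to the risk, because a reader would suppose that attendance was discretionary rather than triggered by the finding.

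**Working it through.** The plan states no PVL or conduction rate, so it has no figure of its own to reproduce. The windows do agree: POD 105 (-15/+30) is 90 to 135, POD 195 (-15/+45) is 180 to 240, and POD 390 (-25/+45) is 365 to 435. The optional interval in Section 9.1.3 is therefore the triggered visit of Section 6.2.1.

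**Inputs, all assumed:**
- p: share with PVL >mild at 3 months
- c: share with a qualifying conduction disturbance, independent of PVL
- s: share of those leaks still >mild at POD 180-240
- q: share with new PVL >mild by then among subjects without it at 3 months

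**Formulas:**
- Attending fraction: f = p + (1 - p)c = p + c - pc
- Percentage among attendees: [ps + (1 - p)cq] / f
- Percentage in the whole cohort: ps + (1 - p)q

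The attendee figure minus the cohort figure equals p(1/f - 1)(s - q). It is positive whenever f is below 1 and a known leak is more likely to be present at POD 180-240 than a new one. That is the basis for saying that the percentage will overstate. With q = 0 the ratio of the two is exactly 1/f, whatever the persistence.

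| p | c | f | Shown if all leaks persist (p/f) | Inflation (1/f) |
|---|---|---|---|---|
| 1% | 30% | 0.307 | 3.3% | 3.3 |
| 3% | 30% | 0.321 | 9.3% | 3.1 |
| 2% | 20% | 0.216 | 9.3% | 4.6 |
| 3% | 10% | 0.127 | 23.6% | 7.9 |
| 1% | 10% | 0.109 | 9.2% | 9.2 |

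Independence matters little here. At p = 3%, c = 30%, f lies between 0.30 (full overlap) and 0.33 (none), so 1/f is 3.0 to 3.3. At p = 1%, c = 10%, f lies between 0.10 and 0.11, so 1/f is 9.1 to 10.

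**Is there a visible rise over POD 90-135?** With q = 0 the attendee figure ps/f exceeds the 3-month figure p only if s > f. For example, take p = 2%, c = 20%, s = 75%. The attendee figure is 0.015/0.216 = 6.9%, against 2.0% at 3 months and 0.02 × 0.75 = 1.5% in the whole cohort.

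**Wider grid, same formulas:** p = 0.5, 1, 2, 5%; c = 5, 10, 20, 30, 50%; s = 25, 50, 75, 100%; q = 0, 0.5%; 160 combinations.
- The attendee figure exceeded the cohort figure in all 160.
- It exceeded the 3-month figure in 144. The 16 exceptions all had c of at least 30% and s of at most 50%.
- With q = 0 and c from 5 to 30%, inflation ran from 3.0 to 18.3 times. At c = 50% it was about 2 times.

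**Dilution:** suppose 25% of non-triggered subjects also attended in the 2%/20%/75% example. Attendance becomes 0.216 + 0.784 × 0.25 = 0.412, and the figure is 0.015/0.412 = 3.6%, still above 2.0% and 1.5%.

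**The case against.** The strongest reply is that the cited sentence in Section 9.1.3 is a collection schedule, not a table shell. The phrase "will be categorized by time interval and valve size" governs continuous echo variables only, and the regurgitation sentence names no interval. This stands as a limit: a by-interval regurgitation table is inferred. It is still the natural reading, and if it is wrong the plan needs to say what the denominator is.

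A second reply is that others may have attended. The Synopsis restricts the visit to triggered subjects, but Section 6.2.1 says only when it is required, and Sections 7.8, 7.9, 8.3 and 9.1.3 call it optional. That dilutes the bias without removing it, as the last calculation shows.

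A third is redaction. Section 9.0 points to detailed analyses through obscured text, and table shells or footnotes may exist there. So the point can only be that the visible plan has no such rule.

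A fourth is that counts accompany percentages, and Section 9.2 promises echo compliance data, so the fall in N would show. It would, but the percentage would stay the same and the reason for the fall would not be given.

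Two stronger readings are tempting. A reader might infer that a PVL peak is certain and due only to who was measured. It is not certain, because it needs persistence to exceed the attending fraction, and real change between visits is also possible. A reader might also infer that gradient and EOA are biased in the same way. Those summaries do come from a selected subset, but neither trigger is defined by gradient or EOA, and nothing in the documents gives a direction.

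**Conclusion.** The point holds in a limited form. If regurgitation is reported by interval, the PVL >mild percentage at POD 180-240 will overstate the cohort share, and it will probably, but not necessarily, stand above POD 90-135 and POD 365-435. The direction follows from the trigger rule, provided that known leaks persist more often than new ones appear. The size does not follow from the documents: the figure of about 3 to 9 times rests on assumed rates of 1 to 3% and 10 to 30%, with independence and no new PVL, and is an illustration rather than an estimate.

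It would be wrong to infer that the primary safety result for PVL is compromised. Section 9.1.2.1 bases late events on linearized rates, and Section 7.6 counts a persisting leak once. What is affected is a descriptive effectiveness display. The change is worth making because it is cheap, but the trial's main conclusion does not depend on it.

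**What to change.** In Section 9.1.3:

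- Leave POD 180-240 out of the cohort by-interval echo and regurgitation tables and out of any trend display.
- State the interval and the denominator for the regurgitation percentages.
- Report POD 180-240 in a separate table labelled as the triggered subset, giving N, the trigger reason, and the same subjects' POD 105 and POD 390 values. Do not split it by valve size: at 1 to 3% of the 934 enrolled, the PVL trigger would supply only about 9 to 28 subjects.
- Describe the visit as triggered rather than optional.

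Section 6.2 says that all subjects had been followed through one year at this revision, so this changes tables and wording, not data collection. No data are lost, and the paired table would show whether the leaks persisted. The cost is a few lines of text and one extra small table, some of whose cells will be sparse.
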